# 8.2.1. Primary Objective and High-Risk Subgroup Analyses

# 8.2.1.1. Inclusion Criteria

Patients had ≥1 inpatient claim or ≥2 outpatient claims (at least 7 days gap between the two outpatient claims) for AF (ICD-9-CM code 427.31; ICD-10-CM: I480-I482, I4891) during 01JAN2013-31DEC2016. The first AF diagnosis claim dates during the identification period will be designated as the index date;

Note: Revised from  $\geq 1$  AF diagnoses based on literature review and clinical rationale to consolidate the diagnosis of AF.

2) Patients had 12-month continuous health plan enrollment with medical and pharmacy benefits (Medicare Part A, B, and D) before the index date and 6-month continuous health

Do not distribute for purposes outside of specific activities related to development of FDAMAs114 compliant pieces. Content within this protocol is subject to change based on communication planning and input by external review committees.

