## 8.3. Variables

All data will be extracted from the Medicare Database (Section 8.4). Baseline variables will be measured for the prior 12 months through the index date (exclusive of the index date). All relevant ICD-9-CM, ICD-10-CM, and CPT codes are available in the Appendix.

Variable a	Role	Operational definition
Age	Baseline characteristic and potential predictor	Age will be defined as of the index date, retained in the dataset as continuous, and divided by the following age groups: 65-74, 75-84, and $\geq$ 85 years.
Sex	Baseline characteristic and potential predictor	A flag will be created for female beneficiaries on the index date and reported as a percentage.
Race/ethnicity	Baseline characteristic and potential predictor	A flag will be created for White, Black, Hispanic, and other races/ethnicities on the index date.
US geographic region	Baseline characteristic and potential predictor	The US will be divided into 5 regions: Northeast, South, North Central, West, and Other. Geographic region will be captured from enrollment data.

Table 1	. Baseline	Variables
---------	------------	-----------

Do not distribute for purposes outside of specific activities related to development of FDAMAs114 compliant pieces. Content within this protocol is subject to change based on communication planning and input by external review committees.

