#### Apixaban

NON-INTER	VENTIONAL	STUDY	PROTOCOL
HOI IN LICE		DIODI	ROTOCOL

Variable a Role		Operational definition		
	and potential predictor			
History of falls Baseline characteristic and potential predictor		A flag will be created for patients with claims for fall(s) in the baseline period.		
Baseline medication use	Baseline characteristic and potential predictor	Individual flags will be created for patients with prescription claims for angiotensin converting enzyme inhibitors, amiodarone, angiotensin receptor blockers, beta blockers, H2-receptor antagonists, proton pump inhibitors, anti-platelets, statins, nonsteroidal anti-inflammatory drugs (NSAIDs), inhibitors of warfarin, inducers of warfarin, dronedarone, digoxin, calcium channel blockers, renin angiotensin system antagonists, glucocorticoids, diuretics, metformin, sulfonylureas, thiazolidinedione, insulin, other diabetes drugs, antiulcer agents, and antidepressant.		
Index dose of NOAC Baseline characteristic		The index dose of the NOAC will be evaluated and categorized as standard (5mg apixaban, 150mg dabigatran, 60mg edoxaban, and 20mg rivaroxaban,) or low dose (2.5mg apixaban, 75mg dabigatran, 30mg edoxaban, and 10 or 15mg rivaroxaban,)		
Baseline all-cause health care Baseline costs characteristic		All-cause health care costs in the baseline period will be computed for inpatient, office, outpatient hospital, ER, pharmacy, DME, SNF, HHA, and hospice costs. Costs will be adjusted to 2016 US dollars using the medical care component of the CPI. Total medical and total health care costs will be calculated.		
Baseline all-cause health care utilization	Baseline characteristic	All-cause health care utilization in the baseline period will be computed for inpatient admissions, office visits, outpatient hospital visits, ER visits, pharmacy use, DME, SNF, HHA, and hospice use.		

a Unless specified, all primary and secondary diagnosis codes will be used.

Do not distribute for purposes outside of specific activities related to development of FDAMAs114 compliant pieces. Content within this protocol is subject to change based on communication planning and input by external review committees.

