# Logistic Regression: Predictors for OAC Treatment/non-treatment (Primary Objectives)

A logistic regression will be used to examine risk factors associated with OAC treatment (OAC, DOAC, or warfarin)/non-treatment with OACs and DOAC treatment/warfarin treatment. Predictor data will be examined during the 12 months baseline period before the index date.

Stepwise model selection will be used to identify risk factors. The final covariate lists will be finalized based on clinical rationale and model fitting.

Odds ratios, p-values, and 95% confidence intervals (CIs) for all model covariates will be provided. Diagnostic tests will be performed for the multivariate models. Hosmer-Lemeshow tests will be performed and the area under the Receiver Operating Characteristic curve will be checked.

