# Inverse Probability Weighting (IPW; Secondary Objectives)

Do not distribute for purposes outside of specific activities related to development of FDAMAs114 compliant pieces. Content within this protocol is subject to change based on communication planning and input by external review committees.

Pfizer Confidential

Page 28 of 37

Apixaban NON-INTERVENTIONAL STUDY PROTOCOL

IPW uses propensity scores to obtain estimates of the average treatment and censoring effect. Propensity scores will be calculated using repeated measures logistic models with: 1) ever-treated with OAC and never-treated with OAC cohorts; 2) each DOAC treated and never-treated with OAC cohorts included in the model, using never-treated patients as the reference (i.e. control cohort). Appropriate correlation structure will be chosen based on the data and clinical rationale.

The propensity score is defined as the probability of a patient receiving OAC/DOAC treatment or being censored conditional on both time-dependent covariates (e.g., comorbidities) and time-independent baseline covariates (age, gender, race, and baseline value for each of the time-dependent variables). The list of variables included in the logistic model will be based on clinical rationale. The propensity score acts as a balancing score among the cohorts.

After calculating the propensity score, the distribution of the propensity scores will be reviewed.

Each patient's weight is equal to the inverse of the probability of their treatment option and censoring (weight=1/propensity score). The numerator of the weight is the propensity score that a patient is on observed treatment/censored in a time period conditional on the baseline covariates. Denominator of the weight is the same propensity score conditional on time-dependent (factors such as CHA2DS2-VASc score, history of bleeding, etc.) and time-independent confounders. If an ever-treated patient has a very low propensity score, a very large weight can be created. Large weights can increase the variability of estimated treatment effect. In order to address this, the weights will be stabilized. Stabilized weights for treatment and censoring will be calculated for each time period of a patient. This reduces the variability of the weights.

$$SW = \prod_{k=0}^{t} \frac{f[A(k) | \overline{A}(k-1), V]}{f[A(k) | \overline{A}(k-1), \overline{L}(k)]}$$

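### The setting of the index AF claim, inpatient or outpatient, is not a listed predictor or confounder, although patients enter by either route and claims-based history stops before the index date

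*Protocol*

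**What the plan says.** - **Entry (Protocol, Section 8.2.1.1, criterion 1).** "Patients had ≥1 inpatient claim or ≥2 outpatient claims (at least 7 days gap between the two outpatient claims) for AF". The index date follows from whichever AF claim comes first: "The first AF diagnosis claim dates during the identification period will be designated as the index date".
- **Baseline window (Section 8.3).** "Baseline variables will be measured for the prior 12 months through the index date (exclusive of the index date". Some Table 1 items are nevertheless index-date attributes: age, sex, race, index year and index dose.
- **Nearest listed variable (Table 1, baseline utilization).** "All-cause health care utilization in the baseline period will be computed for inpatient admissions, office visits, outpatient hospital visits, ER visits". It covers the pre-index year only. Its role is baseline characteristic, without the potential-predictor label that most other rows carry.
- **Primary model (Section 8.7, Logistic Regression).** "Predictor data will be examined during the 12 months baseline period before the index date". On the choice of terms: "The final covariate lists will be finalized based on clinical rationale and model fitting".
- **Weights (Section 8.7, Inverse Probability Weighting).** The propensity model conditions on time-dependent covariates, with comorbidities as the example, and on "time-independent baseline covariates (age, gender, race, and baseline value for each of the time-dependent variables". On the full list: "The list of variables included in the logistic model will be based on clinical rationale".
- **Subgroups and sensitivity analyses (Section 8.8).** The primary objective is examined by CHA2DS2-VASc score and by age. Nothing is examined by setting.

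**The concern.** A patient whose AF is first coded during a hospital stay and one whose AF is first coded at an outpatient contact may differ in how likely an anticoagulant is to be started. They may also differ in their early risk of death, bleeding, stroke and cost. The attribute that separates them is fixed at the index date and comes from the claims that establish eligibility.

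The primary objective is to find predictors of treatment. If setting is not a candidate, any association it has with treatment is either missed or shared out among correlated terms such as age, heart failure or prior bleeding. In objectives 2 to 5, anything setting contributes beyond the adjusted covariates stays in the treated-versus-untreated contrast. Days before the first fill count as untreated time, so an index stay falls on the untreated side.

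**Working it through.** The protocol states no figure on this point, so there is none to reproduce. The check is first of the text, then of scale.

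**1. Is setting anywhere in the plan?**
- Abstract variable list and Table 1: no row for the setting of the index or qualifying AF claim.
- Primary model: predictor data come from the year before the index date. A setting variable would have to be an index-date attribute, as age and index year are, and it is not listed as one.
- Weights: the named baseline covariates are age, gender, race and baseline values of the time-dependent variables. Setting is not named, but the list is open.
- Section 8.8: no analysis by setting.

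**2. What happens to information coded at an index admission?**
- Eligibility uses it. The CHA2DS2-VASc criterion and the valve, venous thromboembolism and transient-AF exclusions all include the index date.
- The baseline flags do not use it. The prior-bleed, prior-stroke and comorbidity flags cover the baseline period, which ends before the index date. Under the Table 1 footnote, primary and secondary codes both count unless specified. An admission for a bleed or stroke with AF as a secondary code could therefore be the index event and set no prior-bleed or prior-stroke flag.
- The weights may use it in part, because their denominator conditions on covariate history from time period 0. That can carry diagnoses from the stay, but not the setting itself.

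**3. Scale for objectives 2 to 5, on assumed inputs only.** For an omitted binary confounder the observed ratio is multiplied by

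B = [p1(RR − 1) + 1] / [p0(RR − 1) + 1],

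where p1 and p0 are the inpatient-index shares in treated and untreated time and RR is the outcome rate ratio, inpatient versus outpatient index. The documents give none of the three. Assumed: p0 of 0.30 to 0.50, p1 differing from p0 by 0.10 to 0.15 in either direction, RR of 1.5 to 3.

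| p0 | p1 | RR | B |
|---|---|---|---|
| 0.30 | 0.15 | 3 | 1.30/1.60 = 0.81 |
| 0.40 | 0.30 | 2 | 1.30/1.40 = 0.93 |
| 0.50 | 0.40 | 1.5 | 1.20/1.25 = 0.96 |
| 0.50 | 0.60 | 1.5 | 1.30/1.25 = 1.04 |
| 0.50 | 0.65 | 3 | 2.30/2.00 = 1.15 |
| 0.30 | 0.45 | 3 | 1.90/1.60 = 1.19 |

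The first and last rows are the extremes of this grid. For comparison, the major bleeding rates used in Section 8.5 give a ratio of 1.4/1.2 = 1.17, so the outer values are of the same order as that planning effect. B is the factor before any adjustment; whatever the weights capture brings it nearer to 1.

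**The case against.** The strongest reply is that covariate choice is left open. Both models defer their final lists to clinical rationale, the weight covariates are given as examples, and a statistical analysis plan that is not shown could add setting. For the weights this stands: nothing bars the variable. It is weaker for the primary model, because the protocol itself itemises the candidates with their roles and sets the predictor window before the index date.

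A reader might infer more than the documents support:

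- *That every baseline variable excludes the index date.* Age, sex, race, index year and index dose are taken at or tied to it. The exclusion bites on claims-based history.
- *That an index admission leaves no trace in any covariate and the two groups cannot be told apart.* The time-dependent covariates in the weights may pick up diagnoses from the stay.
- *That acutely hospitalised patients are being pooled with clinic patients.* The AF criterion specifies no claim position, so an inpatient AF code may be incidental to another admission. The protocol does not equate outpatient with clinic diagnosis either.
- *That entry route and index setting are the same thing.* A patient who qualifies through an inpatient claim may have an earlier outpatient AF claim as the index.

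Section 8.10 also concedes residual confounding and limits the claims to associations, and Section 8.7 allows objectives 2 to 5 to be dropped. Those caveats are fair, but a general caveat is a poor substitute for using a variable already in hand.

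**Conclusion.** The point holds as an inexpensive improvement, and it is firmest for the primary objective. As written, the predictor models cannot assess setting of diagnosis, and diagnoses first coded at an index admission set no baseline flag. The stepwise analysis is not thereby invalid; it leaves out a plausible candidate that is known for every patient.

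For objectives 2 to 5, setting is a potential and partly captured confounder. The factor of about 0.81 to 1.19 rests wholly on assumed shares and rate ratios, spans 1 and ignores what other covariates absorb. It shows that the matter could be material. It does not estimate the remaining bias, and it does not support saying that these comparisons are biased in a particular direction.

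**What to change.** 1. Define the setting of the index AF claim (inpatient versus outpatient or ER) as an index-date variable, on the same footing as age and index year. State how claims from both settings on one date are classed. Record the qualifying route (one inpatient or two outpatient claims) as a separate variable.
2. Add index-claim setting to Table 1 as potential predictor and potential confounder.
3. Include it in the primary logistic models, and tabulate the never-treated share by setting.
4. Include it as a time-independent baseline covariate in numerator and denominator of the weights. A covariate that sits in both is not balanced by stabilised weights, so the outcome models must carry it too: as a stratum or covariate in the Cox models, and as a time-invariant covariate in the GEE cost models, which the protocol already permits.

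The cost is one derived flag from claims already processed for eligibility, plus one table. No new data are needed and eligibility does not change.

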#### Apixaban NON-INTERVENTIONAL STUDY PROTOCOL

- 4. Compare the risk of death among elderly patients treated versus untreated with OACs in the Medicare NVAF population.
- 5. Compare the all-cause health care costs among elderly patients treated versus untreated with OACs in the Medicare NVAF population.

**Study Design:** The study will be a longitudinal retrospective cohort analysis using the US Centers for Medicare & Medicaid Services (CMS) Medicare dataset from 01JAN2012-31DEC2016. The study will designate a 12-month baseline period prior to the identification period (01JAN2013-31DEC2016). This database only includes patients enrolled in fee-for-service (FFS) Medicare; those enrolled in managed-care plans will be excluded. Further, patient eligibility will be based on selection from the database according to the following inclusion and exclusion criteria (sections 2).

**Population:** Elderly patients (aged  $\geq 65$  years) will be required to have  $\geq 1$  inpatient or  $\geq 2$  outpatient medical claims (the 2 outpatient claims are  $\geq 7$  days apart) for AF during the identification period for the primary and secondary objectives. For the primary objective, two mutually-exclusive NVAF patient cohorts will be created: ever-treated with OAC and never-treated with OAC. For the secondary objective assessing clinical and healthcare utilization and costs, treatment status will be a time-varying covariate and ever-treated patients will contribute time-not-on-treatment to untreated effect.

For the primary and secondary objectives, the ever-treated with OAC population cohort will include newly diagnosed NVAF patients who ever initiated oral anticoagulant (OAC) treatment (apixaban, dabigatran, edoxaban, rivaroxaban, and warfarin) during the study period identified from 01JAN2013-31DEC2016. The never-treated with OAC population cohort will include newly diagnosed NVAF patients without any OAC claim from 01JAN2013-31DEC2016.

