For the primary and secondary objectives, the first AF diagnosis date during the identification period will be used as the index date for both ever-treated and never-treated cohorts. Across both ever-treated and never-treated cohorts, all patients will be required to have a  $CHA_2DS_2$ -VASc $\geq 2$  and 12-months of continuous health plan enrollment, with medical and pharmacy benefits before the index date (baseline period). For the primary objective and high-risk subgroup analyses, patients will also be required to have 6-month continuous health plan enrollment, with medical and pharmacy benefits after the index date.

For the primary objective and high-risk subgroup analyses, the following patients will be excluded: an AF diagnosis any time prior to the first AF diagnosis; medical claims indicating a diagnosis or procedure for mitral valvular heart disease or heart valve replacement/transplant;

Do not distribute for purposes outside of specific activities related to development of FDAMAs114 compliant pieces. Content within this protocol is subject to change based on communication planning and input by external review committees.

Apixaban NON-INTERVENTIONAL STUDY PROTOCOL

or use of OACs during the baseline period. For the secondary objective assessing effectiveness, safety, and cost outcomes, patients will be further excluded if they had any of the following: venous thromboembolism; transient AF during the baseline period; pregnancy during the study period; hip/knee replacement surgery within 6 weeks pre-index date; or follow-up period = 0 day. In addition, among patients ever treated with an OAC, those with >1 OAC prescription claim at the index date will be excluded as well.

**Variables:** Baseline demographic and clinical characteristics will include age, gender, race, geographic region, Medicaid dual eligibility, Part-D low income subsidy, Charlson comorbidity index (CCI), CHADS2, CHA2DS2-VASc, HAS-BLED scores, prior bleeding/stroke events, congestive heart failure, diabetes, hypertension, chronic obstructive pulmonary disease, renal disease, myocardial infarction, dyspepsia or stomach discomfort, peripheral arterial disease, transient ischemic attack, coronary artery disease, history of falls, medication use, and index dose of DOAC. Baseline all-cause health care costs and utilization will be included.

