# 8.2. Setting

Ever treated with OAC and never treated with OAC patients will be selected from 01JAN2013-31DEC2016. To ensure access to the patients' complete medical history, they will be required to have continuous health plan enrollment for the 12 months before the first AF diagnosis date/index date (baseline period). Patient data will be assessed from index date until the earliest of death, health plan disenrollment, treatment switch (treated patients), discontinuation (treated patients), or 31DEC2016 (end of study).

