#### Apixaban

Table 2. Clinical and Treatment Pattern Outcome Variables					
Variable	Role	Operational Definition			
Stroke/SE	Outcome	Stroke/SE will be identified using hospital claims with a stroke/SE diagnosis code as the first listed ICD-9-CM or ICD-10-CM code. Stroke/SE will be classified into 3 categories: ischemic stroke, hemorrhage stroke, and SE. Time to stroke/SE will be defined as the number of days from index date to the occurrence of the first stroke/SE requiring hospitalization.			
Major bleeding	Outcome	Major bleeding will be identified using hospital claims with a bleeding diagnosis code as the first listed ICD-9-C or ICD-10-CM diagnosis or procedure code.  Time to major bleeding will be defined as the number of days from index date to the occurrence of the first major bleeding event requiring hospitalization. Major bleeding may be further stratified by gastrointestinal and intracranial hemorrhages and other major bleeding.			
Death	Outcome	Death information from the database will be used. Time to death will be defined as the number of days from index date to death.			
Discontinuation (Treated Patients)	Outcome	Treated patients will be considered to have discontinued if there was no additional refill for the index anticoagulant after 30 days of the previous prescription's run-out date.  The discontinuation date will be defined as the run-out date plus 30 days.			
Time to discontinuation (Treated Patients)	Outcome	Time to discontinuation will be defined as the number of days from the OAC prescription index date to the discontinuation date.			
Switch among anticoagulants (Treated Patients)	Outcome	A switch among anticoagulants will be defined as a prescription filled for non-index anticoagulants within 30 days before or after the run-out date.  Time to switch will be defined as the number of days from the OAC prescription index date to the first prescription date of the switch.			
Time-to-switch (Treated Patients)	Outcome	Time to switch will be defined as the number of days from the OAC prescription index date to the switch date.			

Table 2, Clinic	cal and Treatment Patt	ern Outcome Variables
	cal and frequencine i acc	

Do not distribute for purposes outside of specific activities related to development of FDAMAs114 compliant pieces. Content within this protocol is subject to change based on communication planning and input by external review committees.

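### For patients whose first AF claim is outpatient, follow-up starts before eligibility is settled, so early death is suppressed and stroke and bleeding rates can be inflated

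*Protocol*

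**What the plan says.** Section 8.2.1.1 gives two routes into the cohort: one inpatient AF claim, or "≥2 outpatient claims (at least 7 days gap between the two outpatient claims) for AF", at any time in 2013-2016. The same item sets time zero: "The first AF diagnosis claim dates during the identification period will be designated as the index date".

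The abstract (section 3) carries the diagnosis rule to the outcome analyses, "for AF during the identification period for the primary and secondary objectives", and also the start date: "the first AF diagnosis date during the identification period will be used as the index date for both ever-treated and never-treated cohorts".

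Follow-up and the outcome clocks run from that date. Section 8.2: "Patient data will be assessed from index date until the earliest of death", or the other listed end points. Section 8.3, Table 2: "Time to stroke/SE will be defined as the number of days from index date to the occurrence of the first stroke/SE requiring hospitalization". Major bleeding is timed the same way, and for death "Time to death will be defined as the number of days from index date to death".

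Three further rules bear on the point:

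- Table 2 identifies stroke/SE and major bleeding from hospital claims with the event code listed first. The AF rule names no code position, and the footnote to Table 1 reads "Unless specified, all primary and secondary diagnosis codes will be used".
- The abstract counts an ever-treated patient's time off treatment as untreated.
- The abstract states the 6-month post-index enrolment requirement only for the primary objective and the high-risk subgroups.

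**The concern.** A patient whose first AF claim is inpatient is eligible on day zero. A patient whose first AF claim is outpatient is not. That patient joins the cohort only if a further AF claim follows, yet is counted as at risk from the first one. Two things follow.

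- **Death.** Someone who dies after a single outpatient claim, with no AF-coded admission, never enters. The interval before confirmation is partly selected on survival.
- **Stroke/SE and bleeding.** Someone with a single outpatient claim who is later admitted with a first-listed stroke or bleed, with AF coded lower down, becomes eligible through that admission. It is then scored as an outcome dated from the outpatient claim. A similar patient with no event and no other AF-coded claim is absent from the denominator.

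Secondary objectives 2-4 compare treated with untreated time. If patients not on OAC are confirmed less often, or wait longer off treatment, the distortion differs between the two kinds of time and enters the hazard ratio. Weighting cannot recover people who never entered the data set. With the 100% Medicare database named in section 8.10, precision will be high, so bias of a few per cent will not be hidden by wide intervals.

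**Working it through.** The plan gives no figure for this bias. The check therefore has three parts: the text, a hand calculation, and a simulation under no treatment effect.

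**1. Text: does anything delay entry?**

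- Excluding patients with 0 days of follow-up (section 8.2.2.2) removes only day-zero cases.
- The weights in section 8.7 act on included patients.
- The multivariable Cox and competing-risk analyses in section 8.8 keep the same cohort and clock.
- Censoring at 6 months (section 8.8) concentrates the analysis on the affected window.

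So nothing delays entry.

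**2. Rates from the plan.** Section 8.5 uses stroke/SE rates of 1.6% and 3.7% per year and bleeding rates of 1.4% and 1.2%. As a check on reading them: with hazards −ln(1−p), the ratio is 0.01613/0.03770 = 0.428. Freedman's formula gives 7.849 × (1.428/0.572)² ≈ 49 events. With 4 years of accrual, 4 years of follow-up and 10% annual loss this needs 449 patients, against 450 stated. For bleeding the same model gives 23,528 against 23,674.

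**3. Hand calculation for stroke, extreme case.** Let a share *s* of outpatient-first untreated patients never get a second claim, let AF be coded on 90% of stroke admissions, and allow no other AF-coded admission. Events are kept in the proportion 1 − 0.1*s*, and person-time in roughly 1 − *s*:

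- *s* = 5%: 0.995/0.95 = 1.05
- *s* = 10%: 0.99/0.90 = 1.10
- *s* = 20%: 0.98/0.80 = 1.23 (1.21 by simulation, which also counts the person-time of the single-claim patients who enter)

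This is an upper case. With other AF-coded admissions at 0.2 per year, 40% of deaths having an AF-coded admission and 70% outpatient-first, the ratios fall to 1.02, 1.04 and 1.08. Varying these inputs gives 1.01-1.21.

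**4. Simulation of both kinds of time, true HR 1.0.** True rates per 100 person-years are stroke 3.7 and bleeding 1.2 (section 8.5) and death 10.0 (assumed).

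Base-case inputs, none of them in the documents:

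- 70% outpatient-first
- half ever on OAC, median start 36 days
- median 3 months to confirmation, and 15% of non-OAC patients never confirmed
- AF coded on 80% of admissions
- 40% of deaths with a terminal admission
- other admissions at about 0.2-0.3 per year

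Ranges tried: outpatient-first 0-70%; median confirmation 30 days to 6 months; never confirmed 0-40%; AF coding 30-80%; terminal admission 0-80%; OAC in 50-80%, median start 7 days to 6 months.

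Each cell gives untreated / treated rate (HR):

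| Scenario | Stroke | Bleeding | Death | Death rate, first 90 days |
|---|---|---|---|---|
| Base case | 3.92 / 3.72 (0.95) | 1.27 / 1.21 (0.95) | 9.19 / 9.48 (1.03) | 7.0 |
| All eventually confirmed | 3.75 / 3.72 (0.99) | 1.22 / 1.21 (0.99) | 9.11 / 9.48 (1.04) | 6.9 |
| 40% of non-OAC never confirmed | 4.25 / 3.71 (0.87) | 1.36 / 1.22 (0.89) | 9.35 / 9.48 (1.01) | 7.2 |
| 80% terminal admission, 30% never confirmed | 4.07 / 3.74 (0.92) | 1.31 / 1.20 (0.92) | 10.14 / 9.78 (0.96) | 8.9 |
| All inpatient-first | 3.72 / 3.70 (1.00) | 1.20 / 1.20 (1.00) | 9.98 / 10.04 (1.01) | 10.0 |

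Over all scenarios with outpatient-first patients, the stroke HR is 0.87-1.00. First-90-day death is 5.2-8.9, always below 10. The full-follow-up death HR is 0.96-1.08. When events and time count only from the date the AF rule is met, all rates return to their true values (HR 0.99-1.02, which also shows the simulation noise).

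**5. What a 5% shift would mean.** Assume it multiplies the planned contrast. For bleeding, 1.4/1.2 = 1.17 becomes 1.17 × 0.95 = 1.11, and in the worst scenario 1.17 × 0.89 = 1.04. For stroke, 1.6/3.7 = 0.43 becomes 0.41. Bleeding is the outcome at risk.

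**The case against.** The two-claim rule is a deliberate, referenced choice to firm up the AF diagnosis. Objectives 2-5 are optional (section 8.7), section 8.10 limits the study to associations and already expects residual confounding, and the primary objective is untouched. All of this stands, and it argues against the highest severity. It does not remove the fault, because the secondary analyses, if run, start the clock at the wrong date.

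A reader might infer three stronger things that the documents do not support.

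- **That the distortion falls mainly on untreated time.** With half of patients ever treated, 54-88% of pre-confirmation time is untreated. If 80% start OAC at a median of 7 days, the share is 26-35%. The protocol gives no start-time distribution.
- **That the biases have known, opposite directions: in favour of OAC for stroke and bleeding, against it for death.** Only the early suppression of death is robust. Over full follow-up the death HR fell on either side of 1, because AF-coded terminal admissions bring some deaths back in.
- **That untreated stroke rates are inflated by 5-21%.** That comes from outpatient-first patients alone, with a stroke admission as the only alternative route in. AF-coded admissions for other reasons also qualify under section 8.2.1.1 and put event-free patients into the denominator.

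Two points of reading also matter. The any-position footnote belongs to Table 1, so it supports rather than settles the reading that AF coded second on a stroke admission qualifies. And if the 6-month enrolment rule were meant for the secondary objectives too, early death would be removed altogether.

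**Conclusion.** The point holds in limited form. For outpatient-first patients, the protocol starts follow-up at a date when eligibility is not yet known, and eligibility can be conferred by the outcome admission itself. Early death is suppressed in every such scenario examined. Stroke/SE and bleeding rates before confirmation can be inflated. The null stroke or bleeding HR shifts by about 0-13%, with a base case near 5% in favour of OAC and about 1% if all patients are eventually confirmed. The sign of the effect on full-follow-up mortality is not established.

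The mechanism rests on the protocol's own rules. The size rests on assumed values for the outpatient-first share, time to confirmation, share never confirmed, AF coding on admissions and OAC start, and the documents give none of these for this cohort. Inpatient-first patients are not affected. This should be fixed before the secondary comparisons are run; it is not a flaw in the primary objective.

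**What to change.** For secondary objectives 2-5:

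- Keep the first AF claim as the index date for eligibility, the baseline look-back and new-user status.
- Let each patient enter the risk set only on the date the AF criterion is met: the first inpatient AF claim or the second qualifying outpatient claim, whichever comes first (delayed entry).
- Count person-time, costs and events only after that date.
- Treat a stroke/SE or bleeding admission that confers eligibility as history, not as an outcome.
- Take time-varying treatment status and covariates as of entry.
- Add a sensitivity analysis restricted to patients whose first AF claim is inpatient, where index and entry coincide.

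The primary objective keeps its index date. Keeping the index for the secondary objectives also leaves the exclusions tied to it unchanged, including the one for starting more than one OAC that day.

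The cost is a wording change and an entry date in the start-stop data that the time-varying Cox model already needs. The scientific cost is lost early person-time and events. That includes early on-drug bleeds and strokes in patients who start OAC before confirmation, who then enter already treated. The report should state this and give the number of patients and the person-time removed, by treatment status.
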